## 4.4 Randomization Methods

Treatment allocation will be determined using a cluster-randomized crossover trial design. The order of treatment allocation for each orthopaedic practice (cluster) will be randomly assigned using a computer-generated randomization table. Each site will start with the initially allocated study solution and crossover to the other solution for their second recruitment period. This process of alternating treatments will repeat approximately every 2 months as dictated by the initial randomization. For sites that enroll for more than 1 year, the order of treatment allocation may be reversed after 12 months to ensure equal distribution of each treatment across each calendar month

in the study's duration (**Figure 1**). Randomization will be completed by personnel at the CEO Methods Center at the onset of the trial. Personnel from the Methods Center will notify personnel at each participating clinical site of their treatment allocation order. This will allow each participating clinical site to begin preparing for the first run-in period.

## 4.5 Blinding

The orthopaedic team (including the study coordinators) cannot be blinded to the treatment allocation as the antiseptic solutions are visually distinguishable and these individuals need to lead the implementation of the cluster-crossover protocol at their clinical site. The Adjudication Committee Members and data analysts will be blinded to the study treatment. All interpretation of study results will initially be done in a blinded manner by developing two interpretations of the results. One interpretation will assume treatment A is povidone-iodine, the other interpretation will assume it is CHG. Once the data interpretations for each assumption are finalized, the data will be unblinded and the correct interpretation will be accepted.

## 4.6 Description of the Interventions

## 4.6.1 Initial Run-In Phase

Prior to initiating patient recruitment, each clinical site will begin using their assigned preoperative antiseptic skin solution for eligible open fracture surgeries (run-in period) to ensure that acceptable compliance is met before initiating participant enrollment. Acceptable compliance during the run-in phase will be defined as at least 15 eligible open fracture patients with >90% of eligible patients receiving the allocated antiseptic solution or a minimum of one month in duration. The run-in phase may be extended up to 3 months, as deemed necessary by the CEO Methods Center. Study personnel at each clinical site will document compliance with administering the allocated treatment during the run-in phase and submit this weekly to the CEO Methods Center. Specifically, the weekly reports will include the total number of eligible open fracture patients operated on, the proportion who received the assigned pre-operative antiseptic skin solution, and the proportion who did not receive the assigned pre-operative antiseptic skin solution along with details about the deviations (e.g., name of attending surgeon, solution used, rationale for not using the assigned pre-operative antiseptic skin solution). This portion of the study protocol is for quality assurance during the initial implementation of the trial procedures. Open fracture surgeries reviewed during the run-in phase will not be included in the trial. Similarly, these patients will not be approached for informed consent and no individual patient-level data will be submitted. CEO Methods Center personnel will review the weekly reports with each of the clinical sites and develop strategies, as needed, to ensure acceptable compliance during the run-in phase. This weekly communication will prevent any delays in transitioning to the participant enrollment phase.

## 4.6.2 First Intervention Phase

Once the initial run-in phase is completed, participant recruitment will begin with the clinical sites continuing to use the same pre-operative antiseptic skin solution for all eligible open fracture surgeries for a two-month period. Patients will receive the initially allocated treatment solution for all of their open fracture management surgeries, including repeat planned surgeries, even if a planned subsequent surgery occurs during a recruitment period using the non-allocated solution. Participating clusters will ideally be able to enroll a minimum of 77 open fracture patients per treatment over the total study recruitment duration, and it is anticipated that most recruiting centers will exceed this minimum goal. Methods Center personnel will continue to monitor compliance

with the assigned pre-operative antiseptic skin solution over the enrollment phase and work collaboratively with the clinical sites to minimize cases in which a patient receives the incorrect solution. These monitoring activities will coincide with site-specific procedures to maintain compliance for all patients, even those requiring multiple surgical procedures. If an open fracture requires multiple surgeries and the correct solution is not applied at each procedure, the patient will remain in the study and be analyzed using the allocated solution (ITT principle).

## 4.6.3 Second Intervention Phase

Once the first intervention phase is completed, each site will crossover to the opposite study solution. There will be no run-in phase for the second solution and each site will need to develop local procedures to ensure a successful crossover. Example procedures to minimize carry-forward of first solution into the second solution phase include: 1) removing the bottles of the first solution from the orthopaedic operating rooms; 2) changing study posters and notifications within the operating rooms; and 3) performing the crossover during the middle of the week to provide a few days' notice to the operating room staff and to avoid contamination of recent open fracture patients returning for repeat procedures (e.g., weekend admissions). The enrollment goals and procedures will mirror the first intervention phase. Methods Center personnel will continue to monitor compliance with the assigned pre-operative antiseptic skin solution over the enrollment phase and work collaboratively with the clinical sites to reduce the risk of contamination.

## 4.6.4 Special Considerations for Ongoing Treatment Crossovers

Treatment allocation will continue to alternate between the study solutions, as outlined above, for the remainder of study duration. Each intervention phase will be approximately 2 months in duration, as agreed upon by the local site and CEO Methods Center personnel. The duration may be modified to avoid crossovers on holidays, weekends, and other circumstances that could threaten a successful crossover. The expected recruitment duration for the trial is approximately 24 months; however, some sites may have a shorter total recruitment duration (e.g., a participating site who joins the trial later, high volume clinical sites, etc.). The two-month enrollment periods will help account for seasonal variability in SSI incidence and their associated infectious organisms,  as each crossover period will cover a season. In addition, for those clinical sites enrolling beyond 12 months, the distribution of recruitment periods for each solution may be seasonally matched by reversing the order of the alternating allocation after 12 months of recruitment.

## 4.6.5 Evaluation of Site Performance and Removal of Clinical Sites

After every two recruitment periods (approximately every four months), each site will be evaluated for continued participation in the trial. Sites with <90% of eligible patients receiving the allocated solution, differential adherence between study solutions, <95% follow-up of the primary outcome, <90% follow-up of the secondary outcome, incomplete data submission, or other threats to data quality or the validity of the study may be withdrawn from the trial. In the event a site is withdrawn, data collection will be completed for all enrolled participants and these data will be included in the final study analysis.

## 4.6.6 Application of Pre-Operative Antiseptic Skin Solutions

Each solution will be applied to the injured area in accordance with the Food and Drug Administration (FDA) and Health Canada approved manufacturer's directions for use. While the

application and minimum drying time for both study solutions are very similar, local study personnel will provide standardized in-service (training) for orthopaedic surgeons, operating room technicians, and nurses at each participating hospital prior to the run-in phases for each of the two randomized interventions. This training should include reviewing the manufacturers' directions for use to help minimize incorrect application at clinical sites that may not routinely use both solutions. In addition, the manufacturers may also provide demonstration videos and posters for continued refresher training for each solution.

The study protocol will mandate the antiseptic skin solution to be used in each intervention phase (Sections 4.4, 4.6.1, 4.6.2, 4.6.3, and 4.6.4); however, the protocol will remain pragmatic to variability in other co-intervention steps performed during the entire pre-operative skin preparation process performed in the operating room. Based on individual surgeon preference, this often includes mechanically removing visible dirt or debris with a scrub brush, and/or cleaning the limb with isopropyl alcohol or antiseptic scrub solution. These additional skin preparation steps will be permitted provided that: 1) the final skin preparation step prior to surgical incision is the application of the allocated antiseptic solution; and, 2) participating surgeons continue to use the same skin preparation co-interventions in both intervention phases. Co-interventions that contain the opposite active ingredient from the current intervention phase (e.g., using a chlorhexidine scrub brush during the povidone-iodine intervention phase, or conversely, using a povidone-iodine scrub during the chlorhexidine intervention phase) should be avoided; however, deviations from this recommendation will be permitted in order to maintain pragmatic *flexibility of delivery* and reflect real-world clinical practice. The details of all operating room antiseptic co-interventions will be documented.

The pragmatic nature of the cluster-randomized design will reduce the risk of crossovers between treatment groups because all consecutive patients during each recruitment period will receive the same treatment. Similarly, open fracture patients that require multiple planned surgeries for their injury will receive the same antiseptic skin solution during each subsequent procedure. Methods Center personnel will work with each of the clinical sites to develop strategies for minimizing crossovers. For example, for patients enrolled within 14 days of the anticipated end of a recruitment period or patients requiring multiple surgeries, study personnel will develop local procedures to identify these patients as study participants, and indicate the patient's allocated antiseptic solution in the medical chart and CRFs.

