**Table 1: PRECIS-2 Score** 

Domain	Score	Rationale	
Eligibility	5	Eligibility criteria are very broad and include all fracture patients that would be treated in all hospital environments.	
Recruitment	5	Recruitment of all consenting fracture patients treated at each participating hospital will be performed.	
Setting	4	Recruitment is occurring at multiple sites across the US and Canada; however, since most of the recruiting hospitals are regional referral centers the setting is "mostly pragmatic."	
Organization	The interventions do not need an increase in providers or care delive compared to the usual antiseptic care provided. For each antiseptic solution brief in-service training session will be provided to the clinical sites, as per mew product/procedure that is being introduced into an operating room.		
Flexibility (delivery)	5	The interventions will be delivered in the usual care manner with no advice on allowed co-interventions or strict protocols to ensure compliance.	
Flexibility (adherence)	-	This section is left blank according to PRECIS-2 guidance because the intervention is provided prior to patient consent and individual patient compliance is not an issue. If provider adherence is considered, the study design is rather pragmatic (4) because there will be limited encouragement to follow the manufacturer's directions for use, other than periodic newsletters, investigator meetings, and possible provider survey during the recruitment period.	
Follow-up	5	All study follow-up is consistent with usual care.	
Primary outcome	5	The outcome has been validated by patients as being very relevant to the study participants and it does not require specialized expertise beyond the treating physician for diagnosis.	
Primary analysis	5	All available study data will be used for analysis following the intention to treat principle.	

[figure not shown]

Figure 2: PRECIS-2 Wheel

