- 4) As-treated analyses: The proportion of surgical procedures receiving the incorrect, non-allocated antiseptic solution will be reported. "As-treated" sensitivity analyses will be performed using the solution received as the independent variable. For participants that were treated in a single open fracture surgery, they will be analyzed using the antiseptic solution received. For participants who received multiple open fracture surgeries, two analyses will be performed. First, the antiseptic solution used in their last surgery prior to a study outcome event will define their study treatment. For the second analysis, the antiseptic solution received in the majority of their

fracture surgeries will define their study treatment. Participants who were treated with multiple open fracture management surgeries, but received equal exposure to both treatment solutions (e.g. one surgery with CHG and one surgery with iodine), will be analyzed within their originally allocated treatment group.

- 5) Co-intervention variability: Selective censoring of one or more clusters and / or treatment periods will be performed to further explore between-cluster and between-period variability identified in the primary and secondary outcome comparisons. These analyses will be used to explore the robustness of the study conclusions in the context of measured practice variations in co-interventions that differ between participating sites and / or evolve over the duration of the study recruitment. Results that are sensitive to the removal of a cluster(s) and / or period(s) will be reported, along with potential clinical hypotheses that are supported by the measured clinical practice variation.
- 6) Exploratory SSI definitions: The above analyses (See Section 5.2.2) will be repeated for the primary comparison using the FRI outcome and the CDC definition within 1 year of injury to determine if the study conclusions are sensitive to alternative definitions of SSI.

**Table 8** below shows a summary of the objectives, corresponding outcomes, hypotheses, and methods for each potential sensitivity analysis.

Table 8: Summary of Sensitivity Analysis Plan

	Ohiootivo	Outcome		Hymothosis	34.1.1.64.1.	
	Objective	Name	Type	Hypothesis	Method of Analysis	
1	Different analysis models	SSI / Reoperation	Binary	10% povidone- iodine will be more effective than CHG	Multi-level regression models with different correlation structures	

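### Section 4.6.6 leaves the rule for scrubs containing a study ingredient unreconciled, and the as-treated analysis has no category for two agents within one procedure

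*Combined protocol and SAP*

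**What the plan says.** Section 4.6.6 permits extra steps, such as an antiseptic scrub chosen by the surgeon, under two conditions. The first is that "the final skin preparation step prior to surgical incision is the application of the allocated antiseptic solution". The second is that "participating surgeons continue to use the same skin preparation co-interventions in both intervention phases". The section then turns to "Co-interventions that contain the opposite active ingredient from the current intervention phase", giving an example in each direction, and says these "should be avoided; however, deviations from this recommendation will be permitted in order to maintain pragmatic" flexibility. All antiseptic co-interventions in the operating room are to be recorded.

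Table 1 in Section 3.2 describes delivery as having "no advice on allowed co-interventions or strict protocols to ensure compliance".

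Three later passages use the exposure:

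- Section 4.6.5 lists grounds on which a site may be withdrawn: "Sites with <90% of eligible patients receiving the allocated solution, differential adherence between study solutions", among others.
- Section 5.2.4, item 4, says that as-treated "sensitivity analyses will be performed using the solution received as the independent variable". Single-surgery patients are grouped by the solution received. Multiple-surgery patients are grouped first by the last surgery before an event, then by the majority of surgeries. Ties return to the allocated group.
- Section 5.2.4, item 5, removes clusters or periods to explore variation in co-interventions.

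**The concern.** Section 4.6.6 itself describes antiseptic scrubs as a common part of preparation, so surgeons whose habitual scrub contains one of the two study ingredients are an expected case. For them the same-in-both-phases condition and the recommendation to avoid the opposite ingredient pull in different directions. Sites may settle the matter differently.

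Two consequences follow. Where the scrub is kept, some procedures in one phase involve both agents. Where it is dropped in one phase only, the arms differ in a co-intervention; that weakens the argument in Section 4.7 that each hospital serves as its own control.

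The as-treated analysis exists to reflect what patients actually received. If it cannot tell a dual-agent procedure from a single-agent one, it cannot do that for these patients.

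**Working it through.** **Step 1: the texts of Section 4.6.6 side by side.** Take a surgeon whose usual scrub contains chlorhexidine. An iodine scrub gives the mirror image.

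| Choice | Same in both phases? | Opposite ingredient avoided? | Result |
|---|---|---|---|
| Keep scrub in both phases | Yes | No, in the iodine phase (permitted deviation) | Both agents in the iodine phase |
| Drop scrub in the iodine phase only | No | Yes | Arms differ in scrub use |
| Drop scrub in both phases | Yes, but usual practice is not continued | Yes | Neither problem |

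The section does not say which row is intended. Table 1, with no advice at all, is a further position.

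**Step 2: how the plan handles a dual-agent patient.** Take a single surgery with a chlorhexidine scrub followed by povidone-iodine as the final step, in the povidone-iodine phase.

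- Primary analysis: povidone-iodine, by allocation. This is as designed.
- Section 4.6.5: counted as having received the allocated solution.
- Section 5.2.4, item 4: the exposure variable is the solution received and has no value for two agents, so the patient falls under one solution. The last-surgery and majority rules likewise give each procedure one label. The tie rule concerns mixing across surgeries and also returns the patient to one group.
- Section 5.2.4, item 5: acts on clusters and periods, not on individual procedures.
- The opening of Section 5.2.4 says the listed analyses may be conducted, so even these are not firm.

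**Step 3: size.** The plan gives no figure for dual exposure. Inputs are the baseline risk of 12.5% and risk ratio of 0.65 (Section 5.1), 1,400 patients before the 10% increase (Table 5), and 4% use of both agents in the earlier open-fracture trial (Section 1.7).

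Plan figures first: 0.125 × 0.65 = 0.08125. The difference is 4.375 points, which Section 5.1 gives as approximately 4%. The odds ratio is (0.08125/0.91875)/(0.125/0.875) = 0.62, as in Table 5.

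Assume a share f in each arm receives both agents and carries the midpoint risk, (0.125 + 0.08125)/2 = 0.103125. With f = 0.04:

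- Chlorhexidine arm: 0.125 − 0.04 × 0.021875 = 0.124125
- Povidone-iodine arm: 0.08125 + 0.04 × 0.021875 = 0.082125
- Difference: (1 − 0.04) × 4.375 = 4.2 points
- Risk ratio: 0.082125/0.124125 = 0.66

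Other assumptions at 4%:

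- Only the povidone-iodine arm is affected, and its dual-agent patients lose the whole benefit: 0.083/0.125 = 0.664.
- Only the chlorhexidine arm is affected, and its dual-agent patients gain the whole benefit: 0.08125/0.12325 = 0.659.

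An unclustered pooled two-proportion calculation (two-sided 0.05, 700 per arm) gives power of 76.8% with no dual exposure and 73.4% at f = 0.04 under the midpoint assumption. The level is not the trial's planned power, which comes from a clustered simulation; only the change of about 3 points is of interest.

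**The case against.** The best defence is that Section 4.6.6 can be followed. Sameness across phases is a condition, whereas avoiding the opposite ingredient is only a recommendation with deviations expressly allowed. A surgeon who keeps the scrub in both phases meets both conditions and uses a permitted deviation. This stands in part: the statements are in unresolved tension and are not two binding rules that exclude each other. It does not explain what a surgeon who follows the recommendation should do about the condition.

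Several stronger readings are tempting, and the documents do not support them:

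- A reader might infer that a povidone-iodine patient who also received chlorhexidine is treated as a pure povidone-iodine case. No section says so, the allocated solution must still be applied last, and the issue is the same for chlorhexidine patients who receive iodine.
- A reader might infer that the primary analysis is compromised. It is by allocation, and the stated question is which solution works better with other steps left to usual practice.
- A reader might infer that the exposure goes unseen. Co-interventions are recorded, Section 4.7 has them monitored every four months, and item 5 would pick up scrub habits that are specific to a site. What is missing is a rule at the level of the procedure.
- A reader might put in larger shares: 10% would give a risk ratio of 0.68 and 30% would give 0.74. The documents offer no source for any share above 4%. Even the 4% describes practice in another trial, with no sign that an avoidance recommendation applied.

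Sections 5.2.1 and 5.2.2 also defer detail to a separate statistical analysis plan. The missing definition could go there, but the present text does not supply it.

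**Conclusion.** The point holds as a gap in wording and classification. Section 4.6.6 contains statements that must be reconciled for surgeons whose scrub contains either study ingredient, and Table 1 does not match that section. The as-treated analysis would count dual-agent procedures as exposure to one solution.

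The likely size is small on the only documented figure: the risk ratio moves from 0.65 to about 0.66 and the difference from about 4.4 to 4.2 points. This rests on four assumptions:

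- the 4% carries over to this trial;
- it can be read as a share of patients;
- dual-agent patients carry the average risk;
- 0.65 describes single-agent exposure, which Section 5.1 does not state.

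The true frequency is unknown, which is a reason to report it. If scrubs are dropped in one phase only, neither the size nor the direction of the effect can be derived from the documents.

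**What to change.** 1. Reconcile the statements in Section 4.6.6 so that a surgeon whose routine scrub contains a study ingredient can tell what applies, and bring Table 1 into line. The choice of preparation rule belongs to the sponsor.
2. Using the co-intervention details already required, classify each procedure as allocated agent only, opposite agent only, or both, and report the counts by arm.
3. In Section 5.2.4, item 4, make dual-agent procedures their own category. Add one as-treated analysis excluding dual-agent participants. Define exposure over a pre-specified window that is the same for participants with and without events, for example the first fracture surgery. A window ending at the event would treat the two groups differently and would tend to remove patients with more surgeries.
4. Do not add dual-agent procedures to the site-withdrawal criteria in Section 4.6.5, because that would penalise a practice that Section 4.6.6 permits.

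The cost is protocol and analysis-plan wording plus one extra analysis on data already collected. The restricted set is smaller, is not randomised, and may under-represent more severe injuries, so it can serve only as a sensitivity analysis.
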